### 9.2.2 Exclusion criterion/criteria

Patients receiving Xofigo in a clinical trial.

### 9.2.3 Withdrawal

Not applicable.

### 9.2.4 Replacement

Not applicable

### 9.2.5 Representativeness

Currently there are in total 15 nuclear medicine centers that will provide Xofigo treatment in Sweden. All these 15 nuclear medicine centers are commercially licensed and they have a close collaboration with the Oncology Department in the same hospital. This study will cover all patients receiving treatment of Xofigo at these 15 nuclear medicine centers. Therefore it is expected that this study will cover all potential Xofigo users in Sweden (highly representative) at least in the beginning of the study period. There is a chance that more centers will start treatment with Xofigo in the later part of the study period. We will add later certified centers to the study.

### 9.2.6 Visits

Not applicable

## 9.3 Variables

- Study variables will be collected from two pre-existing secondary data sources: 15 Nuclear medicine centers in Sweden and the Swedish National Cancer Registry. Study variables include patients' age, gender, cancer diagnosis/treatment indication, dosage level (kBq/kg) and number of doses.

### 9.3.1 Variables to determine the primary endpoint(s)

The variables for primary objectives are:

- Gender
- Age
- Indication for treatment (cancer diagnosis)
- Dosage level (kBq/kg) and number of doses

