#### 4 Abstract

Acronym / Title	A Drug Utilization Study of Xofigo use in Sweden
Protocol version identifier	V 2.0
Date of last version of protocol	10-Oct-2014
IMPACT study number	17399
Study type	 non-PASS  PASS      Joint PASS:  YES  NO
Author	[name], Department of Clinical Science, Intervention and Technology, Karolinska Institutet
Rationale and background	
 
▪ Prostate cancer is the second most common cancer and the sixth leading cause of cancer mortality among men worldwide. A large number of men has disseminated disease at diagnosis or has a relapse after treatment with curative intent. Bone metastases and their clinical sequelae are among the most frequent and debilitating complications in patients with castration resistant prostate cancer (CRPC). Xofigo, a well-tolerated alpha-emitter with a half-life of 11.4 days, is a calcium mimetic that naturally self-targets to areas of increased bone turnover in bone metastases. It emits high-energy alpha particles of short range (less than 100 µm) that produce a potent and highly localized cytotoxic effect in the target areas. Xofigo was approved in the European Union on November 13, 2013 for the following indication: Xofigo is indicated for the treatment of adults with castration-resistant prostate cancer, symptomatic bone metastases and no known visceral metastases. Xofigo is contraindicated in women who are or may become pregnant. Xofigo can cause fetal harm when administered to a pregnant woman. Xofigo has not been tested on children. The purpose of this study is to evaluate use of Xofigo including potential off-label use in the post marketing setting.
 

Research question and objectives
	
The objective of this study is to evaluate the extent of potential off-label use of Xofigo in Sweden.
 
This study will include all patients for whom a medical decision has been made to treat with Xofigo. In particular, this study is designed to evaluate the use of Xofigo in
 
 
• Men with mCRPC
 
• women.
 
• children.
 
• Patients with bone metastasis but having a diagnosis of other cancer than CRPC.
 
• Patients with repeated courses of treatment or in excess of those recommended in the label.
 

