Xofigo was approved in the European Union on November 13, 2013 for the following indication: Xofigo is indicated for the treatment of adults with castration-resistant prostate cancer, symptomatic bone metastases and no known visceral metastases. Xofigo is contraindicated in women who are or may become pregnant. Xofigo can cause fetal harm when administered to a pregnant woman. Xofigo has not been tested on children. The licensed dosage of Xofigo is 50kBq (1.35 microcurie) per kg body weight given at 4 weeks interval for six injections

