## 8 Research questions and objectives

This study will include patients for whom a medical decision has been made to treat with Xofigo.

The primary objectives in this study are:

- To estimate the use of Xofigo for men with mCRPC
- To estimate the use of Xofigo in women.
- To estimate the use of Xofigo in children.
- To estimate the use of Xofigo in patients with bone metastasis but having a diagnosis of other cancer than castration resistant prostate cancer.
- To estimate the use of Xofigo in dosage level (kBq/kg) and number of doses outside recommendations.

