## 9 Research methods

### 9.1 Study design

This is a single-arm descriptive observational drug utilization study based on secondary data collection of patients treated with Xofigo in Sweden.

This study will include patients receiving treatment of Xofigo at certified nuclear medicine centers across Sweden during a two year period. It will consist of mCRPC patients and potentially some other patient groups in whom Xofigo may be used off-label including women, children, cancer patients having bone metastasis with a diagnosis other than CRPC, and patients with repeated courses of treatment or in excess of those recommended in the label. This study will be based on data extracted from two pre-established data sources: 15 nuclear medicine centers across Sweden and the Swedish National Cancer Registry.

The Personal Identification Numbers (PINs) for all patients treated with Xofigo at the 15 Nuclear Medicine Centers in Sweden will be extracted and recorded manually by the investigator. The PIN is a unique identification number for all inhabitants in Sweden including information on gender and birth year. Information on treatment indication, dosage level (kBq/kg) and number of doses will be obtained from the nuclear medicine centers. Information on if the patient is included in a clinical trial will also be obtained.

Through a record-linkage between the information provided from the Nuclear Medicine Centers and the Swedish National Cancer Registry based on the individuals' PINs, the cancer diagnosis will be confirmed.

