### 9.1.1 Primary endpoint(s)

The primary endpoints are:

- The use of Xofigo in mCRPC
- The use of Xofigo in women.
- The use of Xofigo in children.
- The use of Xofigo in patients with bone metastasis but having a diagnosis of other cancer than mCRPC.
- The use of Xofigo in dosage level (kBq/kg) and number of doses outside recommendations.

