### **9.3.6 Exposure / treatment**

The dosage level and the number of doses..

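### Repeated courses are a named target in the abstract and section 9.1, but sections 8 and 9.1.1 omit them and a dose count without injection dates cannot identify them

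*Protocol*

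**What the plan says.** The abstract (section 4) lists the groups whose use of Xofigo the study is designed to evaluate. One of them is "Patients with repeated courses of treatment or in excess of those recommended in the label". Section 9.1 names the same group among those in whom off-label use may occur: "patients with repeated courses of treatment or in excess of those recommended in the label".

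The formal statements are narrower. The dosing objective in section 8 is "To estimate the use of Xofigo in dosage level (kBq/kg) and number of doses outside recommendations", and the matching primary endpoint in section 9.1.1 is "The use of Xofigo in dosage level (kBq/kg) and number of doses outside recommendations". Neither mentions courses.

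The data to be collected follow the narrower wording. Section 9.3 states: "Study variables include patients' age, gender, cancer diagnosis/treatment indication, dosage level (kBq/kg) and number of doses". Section 9.3.1 gives "Dosage level (kBq/kg) and number of doses", and section 9.3.6 gives "The dosage level and the number of doses". The variable list in the abstract and the description of centre data in section 9.1 name the same two dosing items.

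Section 7 describes the licensed regimen as 50 kBq "per kg body weight given at 4 weeks interval for six injections". That description has three parts: a level, an interval and a count.

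**The concern.** A course is a pattern in time. To recognise a second course, one has to know when injections were given, or the source has to label the course. The listed variables provide neither, so a group that the protocol names twice cannot be separated out from the data it specifies.

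A later analysis plan cannot repair this. It can define what gap between injections marks a new course, but it cannot apply that definition to dates that were never transcribed. The data are extracted by hand from the centres and entered on a standardized CRF (sections 9.1 and 9.8.1), so what is left off the variable list is likely to need a second round of extraction. Annex 1 lists no stand-alone documents, so the protocol points to no other place where dates are required.

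At stake is one of the off-label questions that the study was set up to answer. The other groups (women, children, other cancers, dosage level, dose count) are not affected by this point.

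**Working it through.** There is no sample-size or power figure to reproduce. The study is descriptive, and the approximately 200 patients in section 9.5 are a market expectation. The check compares targets with variables and then asks what a total count can show.

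**Step 1: targets against variables.**
- Repeated courses: named in the abstract and section 9.1; absent from sections 8 and 9.1.1. No date, course number, or course start or stop in the abstract's variable list or in sections 9.1, 9.3, 9.3.1 or 9.3.6.
- Number of doses beyond the label: named in all four places; the dose count measures it.
- Interval between injections: part of the regimen described in section 7; not named as an objective or endpoint; not collected.

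Item 5.3 of the ENCePP checklist (Annex 2) answers yes to exposure being classified by time windows. The body of the protocol contains no such classification. This is a minor inconsistency that points the same way.

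**Step 2: what a total count reveals.** Let a patient have two courses of a and b injections, each from 1 to 6. The upper limit of six is the label count in section 7. The patient is flagged only if a + b > 6.
- All ordered patterns: 6 × 6 = 36.
- Patterns with a + b ≤ 6: a total t can arise in t − 1 ways, so for t = 2 to 6 the number is 1 + 2 + 3 + 4 + 5 = 15.
- Patterns with a + b > 6: 36 − 15 = 21.

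The 15 patterns, for example 3 + 3 = 6, look the same as one course within the label count. The 21 are flagged as exceeding that count; a second full course, 6 + 6 = 12, is among them. Even so, the count alone cannot say whether 12 injections were two courses or one prolonged course. These are counts of patterns. The documents give no information on how often any of them occurs.

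**Step 3: the inclusion window.** Section 9.2.1 includes patients with data recorded between 01 July 2014 and 30 June 2016. Six injections at 4-week intervals span 5 × 28 = 140 days.
- 01 July 2014 minus 140 days is 11 February 2014. A full course begun from that date until the window opened has injections on both sides of the opening or ends on the opening day.
- 30 June 2016 minus 140 days is 11 February 2016. A full course begun after that date, but within the window, runs past the close.

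The protocol does not say whether injections before or after the window count, so the total itself is ambiguous for these patients.

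**Step 4: size of the extra transcription.** 200 patients × 6 injections = 1,200 lines at most if no one exceeds a label-length course; patients with more injections would add to this.

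**The case against.** The strongest reply is that the formal endpoint can be measured as written. Sections 8 and 9.1.1 ask about dosage level and number of doses, and the variables match that wording exactly. This stands: no primary endpoint in section 9.1.1 fails on this account. It leaves the mismatch open, however, because the abstract says the study is designed to evaluate repeated courses.

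The second reply is that the named group also covers use in excess of the label, which a count above six shows directly. This stands too, and it limits the point to recognising repeat courses as such and to those totalling six or fewer.

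Third, dates probably exist at the centres, since applying the inclusion window needs some treatment date, and the CRF, which is not shown, may have a field for them. That is plausible and makes the remedy cheap, but the protocol does not require the dates to be recorded.

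Some stronger readings are tempting and are not supported:
- A reader might infer that a single averaged dosage level is kept per patient, so that one deviating injection is diluted. The protocol does not say whether the level is recorded per injection or per patient.
- A reader might take checking of the 4-week interval to be a failed aim. The interval appears only in the background description of the licence.
- A reader might fear that the check for multiply documented patients in section 9.8.1 deletes second-course records, or that the report will state that few repeat courses occurred. The text says neither.

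**Conclusion.** The concern holds in a limited form. The protocol names repeated courses as a group of interest in two places, omits them from its objectives and endpoints, and lists exposure variables that cannot identify them. Use beyond six injections remains visible. What is lost is the distinction between a second course and a prolonged one (21 of 36 patterns), and any sign at all of repeat courses totalling six or fewer (15 of 36).

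The conclusion rests on two assumptions: that the variable lists describe what will be transcribed, and that each of two courses has one to six injections. The first could be overturned by a CRF that carries dates; in that case the protocol still needs to list them. No statement about the number of patients affected is possible from the documents. The change should be made before extraction, but the defect does not undermine the rest of the study.

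**What to change.** - In sections 9.3.1 and 9.3.6, add the date and the administered kBq/kg of each injection, linked by PIN across centres so that a patient treated at two centres has one injection history. This also settles whether the level is recorded per injection.
- Define a repeated course operationally, in terms of those dates, before extraction starts. This is a rule for classifying data and implies nothing about how patients should be treated.
- State whether injections given before 01 July 2014 or after 30 June 2016 are counted for patients whose treatment straddles the window.
- Reconcile sections 8 and 9.1.1 with the abstract and section 9.1, so that all four say the same thing about repeated courses.
- Correct checklist item 5.3, or support it with the new variables.

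The cost is one extra CRF line per injection, taken from records that are being opened in any case: at most about 1,200 lines for 200 label-length courses, with double entry under section 9.6. As a by-product, the dates would allow the interval between injections to be described, without making it an objective.

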### 9.3.2 Variables to determine the secondary endpoint(s)

Not applicable.

### 9.3.3 Demography

For demographic / socio-demographic assessment, the following data will be recorded:

- Year of birth
- Gender

### 9.3.4 Co-morbidities (medical history, concomitant diseases)

Not applicable

### 9.3.5 Prior and concomitant medication

Not applicable

### **9.3.6 Exposure / treatment**

The dosage level and the number of doses..

### **9.3.7 Assessment of therapy**

Not applicable.

## **9.4 Data sources**

Two pre-existing secondary data sources will be used for the conduct of this study: 15 nuclear medicine centers in Sweden and the Swedish National Cancer Registry

Investigators will collect data of exposed patients from 15 nuclear medicine centers. Information extracted from the nuclear medicine centers will be linked with Swedish National Cancer Registry via the PINs. Each patient will be identified by a unique central patient identification code, which is only used for study purposes. For the duration of the study and afterwards, only the investigator is able to identify the patients based on the patient identification code. It has been shown that the prostate cancer diagnosis in The Swedish National Cancer Registry has a completeness of 98% .

## **9.5 Study Size**

The study size is depending on the market penetration of the product. It's expected that approximately 200 CRPC patients will receive Xofigo in Sweden in a two year period. The study is population based and should cover all patients who will receive Xofigo from all nuclear centers that are commercially licensed in Sweden (15 nuclear centers so far). Under the circumstances that the number of study sites or subjects are limited, the current study can be considered for an extension of another year (conditioning on that the market penetration is favorable). If additional nuclear centers become commercially licensed at a later time, they can be considered to be added to this study when it's necessary. The estimated sample size will be updated and communicated to the Agency in relation to PSUR/PBRER reporting schedule. Alternatively, a similar study in another European country is under evaluation. Whether such a study is feasible would depend on results from the feasibility assessment.

## **9.6 Data management**

STATA 13.1 will be used as software for statistical analysis (this is the standard statistical package used at the Karolinska Institutet, Sweden). Paper-based CRF will be used to record PINs. Data will be entered into the database twice by different persons to identify potential human errors. Data will be matched with information from the Swedish National Cancer Registry. In case of non-match, the CRF will be reviewed manually. Information on the database is available upon request.

Information on quality control are referred to section 9.8.

## 9.7 Data analysis

### 9.7.1 Statistical considerations

Statistical analyses will be of descriptive nature. The study is not aimed to confirm or reject pre-defined hypotheses.

All variables will be analyzed descriptively with appropriate statistical methods: categorical variables by frequency tables (absolute and relative frequencies) and continuous variables by sample statistics (i.e. mean, standard deviation, minimum, median, quartiles and maximum). Patients receiving at least one dose of Xofigo will be included in the analysis. Whenever possible, Data will be stratified by subgroups (e.g. age, gender).

Sample size and disposition information by analysis time point will be displayed in a frequency table.

## 9.8 Quality control

### 9.8.1 Data quality

All variables will be recorded in a standardized CRF. Data will be entered twice by different persons in the EDC to identify errors of typing. After data entry, missing or implausible data will be queried and the data will be validated. A check for multiple documented patients will be done. Data will be matched with information from the Swedish National Cancer Registry. In case of non-match investigators will review the CRF manually.

National and international data protection laws as well as regulations on observational studies will be followed.

### 9.8.2 Quality review

Source data verification will be conducted among a subset of patients randomly selected (at least 10 % of all sites/patients). The purpose of this validation process is to review the documented data for completeness and plausibility, adherence to the study protocol, and verification with source documents. It will be carried out by research staff at our institution with education in study monitoring.

### 9.8.3 Storage of records and archiving

The data will be stored inside firewalls on campus of Karolinska Institutet, in locked rooms, as established in the legal agreement between the Karolinska Institutet and Bayer Healthcare.

### 9.8.4 Certification/qualification of external parties

Not applicable

## 9.9 Limitations of the research methods

There is a risk of missing data if the nuclear medicine centers does not register every patient receiving Xofigo treatment. This risk can be reduced by site visits and a good communication plan during the

research project. There is a risk that communication with the nuclear medicine centers could influence prescribers' decisions or behavior. Diagnosis of the treated patients will be confirmed by information from the Swedish National Cancer Registry. The Swedish National Cancer Registry is of good quality but has a lag time period to include the necessary information. Therefore, the investigators have extended the time for completing the final report to 17 month after the study ends.

## **9.10 Other aspects**

# **10 Protection of human subjects**

## **10.1 Ethical conduct of the study**

This study is an observational study where Xofigo is prescribed and administered in routine clinical practice setting. There is no assignment of a patient to a particular therapeutic strategy. The treatment decision falls within current practice and the prescription of the medicines is clearly separated from the decision to include the patient in the study. No additional diagnostic or monitoring process is required for participation or during the study. Epidemiological methods will be used to analyze the collected data. This study has no ethical concern.

## **10.2 Regulatory authority approvals/authorizations**

ICH-GCP guidelines will be followed whenever possible. Good Pharmacoepidemiology Practices will be followed for the conduct of this study. Recommendations given by other organizations will be followed as well (e.g. EFPIA, ENCePP).

In addition, the guidelines on good pharmacovigilance practices (GVP) will be followed.

## **10.3 Independent ethics committee (IEC) or institutional review board (IRB)**

Documented approval from appropriate IECs/IRBs will be obtained for all participating centers prior to study start.

## **10.4 Patient information and consent**

An approval from IEC is in accordance with regulations and investigators will seek ethical permit without patient consent given that the study is based on secondary data collection and the IEC usually approve waiver from informed consent in this type of study. The patients will remain anonymous to the sponsor.

## **10.5 Patient insurance**

In this study, data on routine treatment of patients in daily practice are documented and analyzed with the help of epidemiological methods. Treatment including diagnosis and monitoring of therapy follows exclusively routine daily practice. Current medical daily practice is observed, and for the patient no risks beyond regular therapy exist – there is no additional hazard arising from study participation. As no study

related risks exist, there is no need to protect the patient additionally by a patient insurance. The general regulations of medical law and the professional indemnity insurance of the investigators and, respectively, the institutions involved provide sufficient protection for both patient and investigator. No study medication will be provided to participants. Thus, product insurance is covered by the existing product liability.

## 10.6 Confidentiality

Bayer as well as all investigators ensure adherence to applicable data privacy protection regulation. Data are transferred in encoded form only. The entire documentation made available to Bayer does not contain any data which, on its own account or in conjunction with other freely available data, can be used to re-identify natural persons. The investigators are obligated to ensure that no documents contain such data.

All records identifying the subject will be kept confidential and will not be made publicly available. Patient names will not be supplied to the sponsor. If the patient name appears on any document, it must be obliterated before a copy of the document is supplied to the sponsor. Study findings stored on a computer will be stored in accordance with local data protection laws.

The investigator will maintain a list to enable patients' records to be identified in case of queries. In case of a report of a serious adverse event (SAE), the responsible pharmacovigilance person may ask for additional clarification. In that case, the company is not allowed to directly contact the patient. All additional information will be provided by the investigator.

